5.5.3 Safety

More than 1,500 subjects were exposed to different doses (25, 50, 75, 100, 200, 400 mg) of linzagolix from 12 completed and 3 ongoing clinical studies. Ongoing studies include two Phase 3 studies for the indication of heavy menstrual bleeding associated with uterine fibroids.

Repeated once daily dosing at up to 700 mg linzagolix was safe and well-tolerated by premenopausal healthy volunteers. In endometriosis patients, doses up to 200 mg once daily for up to 24 weeks of treatment were well tolerated.

Hepatic impairment had no relevant effect on total plasma linzagolix exposure. In women with severe hepatic impairment (Child-Pugh C), 2- to 3-fold unbound mean exposures were recorded. In hepatic impaired subjects, a single dose of 200 mg was well tolerated.

Renal impairment had no relevant effect on total plasma linzagolix exposure. In women with severe renal impairment (eGFR <30 mL/min/1.73 m²) or end-stage renal disease, approximately 2-fold unbound mean exposures were recorded. In renal impaired subjects, a single dose of 200 mg was well tolerated.

The expected side effects of linzagolix are disturbances of the menstrual cycle and hypoestrogenic adverse events (AEs) (metrorrhagia and hot flush).

In the Phase 2b Edelweiss trial, changes from baseline to week 24 in BMD were measured by dual-energy X-ray absorptiometry (DXA) scan, using central reading. Partial E2 suppression achieved with linzagolix 75 mg was associated with a mean percent change from baseline in spine BMD (the site of

greatest bone loss) of -0.8% (95% CI -1.57, -0.03) after 6 months of treatment, while achieving improvement of the conditions in the majority of patients. As expected, full E2 suppression with linzagolix 200 mg lowers BMD by more than 2.5%, which indicates the need for a low dose ABT for use beyond 6 months.

In multiple-dose studies, a dose-dependent occurrence of hot flush was observed (14.63%, 27.27%, 27.8%, 30% and 40.7% at 50 mg, 75 mg, 100 mg, 150 mg and 200 mg linzagolix, respectively). In the Phase 2b Edelweiss trial, a moderate proportion of patients reported a dose-dependent increase in hot flush (at week 12, placebo: 10.9% reporting at least one hot flush; 75mg: 18.4%; 200 mg: 42.1% - at week 24, 75 mg: 19.0%; 200 mg: 45.6%).

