13.5.5 Safety Analysis

The safety and tolerability profile will be assessed versus baseline conditions and differences between treatment groups and descriptive statistics will be produced for both values and change from baseline, where applicable.

Extent of exposure and compliance to treatment will be evaluated.

Concomitant medications will be summarized using the World Health Organization (WHO) Drug Dictionary with frequencies and percentages for each treatment group. All medications administered between the date of the first dose of study drug and the date of the last dose of study drug, inclusive, (i.e., all medications starting or ongoing during the time interval) will be included. Thus, all medications with an end date prior to the first study drug dose will be excluded from the summary table.

An analysis of the TEAEs will be done. AEs will be summarized using the Medical Dictionary for Regulatory Activities tabulated by (MedDRA) dictionary preferred term and system organ class. TEAEs will be summarized with frequencies and percentages for each treatment group. TEAEs are defined as AEs with a start date on or after the first dose of study drug. Adverse events starting more than 30 days following discontinuation of study drug will not be included in summaries of TEAEs but will be summarized separately as post-treatment AEs. Tabulations by severity and drug-relatedness will also be made.

Laboratory parameters values will be summarized for each visit for each treatment group including within-group changes from baseline. Evaluation of shifts for changes from baseline according to the normal range will be provided.

BMD values and corresponding Z-scores will be summarized at baseline and at Month 6 for each treatment group, using the observed data. The within-group percent changes from baseline for BMD values will also be summarized, including 2-sided 95% confidence intervals. Categorical summaries of percent change from baseline will also be produced. The percent changes from baseline to Month 6 will be compared between each of the linzagolix groups and the placebo group via analysis of co-variance with treatment group as the main effect (three values) and including the baseline as a covariate. Sub-group analyses based on demographic and baseline characteristics will be performed for BMD, and will be specified in the SAP. The Safety Analysis Set shall be used when summarizing safety data.

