4. STATISTICAL METHODS

4.1. Sample Size Justification

The planned sample size for this study is 150 subjects per treatment group (450 subjects in total).

An overall two-sided type I error of 0.05 will be used. As there are two linzagolix versus placebo comparisons, Bonferroni corrected p-values will be produced (raw p-values will be multiplied by two prior to comparing to 0.05). The planned sample size considers the hierarchical, fixed sequence testing of the ranked secondary endpoints as well as the co-primary endpoints. The assumptions used for the sample size calculations are based on analyses of clinically meaningful reduction in pain with a stable or decreased use of analgesics from the Phase 2b Edelweiss study. Calculations were performed using East[®] 6.5 software.

One hundred and fifty (150) subjects per treatment group will provide a power greater than 95% to reject the null hypothesis for both co-primary endpoints for either treatment group, assuming a placebo response rate of 14.6% and an active treatment response rate of 48.6% (75 mg, Edelweiss Phase II study results) or 64.7% (200 mg, Edelweiss Phase II study result) for DYS, and a placebo response rate of 18.8% and an active treatment response rate of 42.1% (75 mg, Edelweiss Phase II study result; the response rate for 200 mg in Edelweiss was lower but was inconsistent with the other doses and other timepoints for the same dose and so was not used) for NMPP. In addition, 150 subjects per treatment group provides 85% power to reject the null hypotheses for all the ranked secondary endpoints based on the observed results from the placebo and 200 mg treatment group in the Edelweiss study.

The values used for the sample size calculations assume that these responses rates are what would be seen on average when under treatment including taking into account any subjects who might withdraw from treatment early; therefore the calculations do not need to be further adjusted for dropouts.

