4.2.5. Multiple Comparisons/Multiplicity

All statistical hypothesis tests and confidence intervals will be two-sided. To maintain an overall type I error rate of 0.05, as there are two linzagolix versus placebo comparisons, Bonferroni corrected p-values will be produced (raw p-values will be multiplied by two prior to comparing to 0.05), along with corresponding 97.5% confidence intervals.

The two co-primary efficacy endpoints will be clinically meaningful reduction from baseline over the last 28 days of randomized treatment up to the Month 3 visit (i.e., the 4-week period preceding the Month 3 visit) in the mean daily assessment of DYS and of NMPP measured on a VRS, along with a stable or decreased use of analgesics for EAP.

The primary objective will be assessed by testing the following two-sided hypotheses for each co-primary endpoint, for each linzagolix group versus placebo separately:

Null hypothesis (H0): There is no difference in the odds of subjects meeting the primary endpoint for the active treatment group compared to placebo, that is, the odds ratio (OR) equals 1.

Sponsor:	ObsEva		
Protocol:	18-OBE2109-003		
Document Version No.:	V5.0		

H0: OR =1

Alternative hypothesis (H1): There is a difference in the odds of subjects meeting the primary endpoint for the active treatment group compared to placebo, that is, the OR is not equal to 1.

H1: OR ≠ 1

Where odds are equal to the proportion of subjects meeting the endpoint divided by proportion of subjects not meeting the endpoint.

Each linzagolix group will need to demonstrate a statistically significant difference for both co-primary endpoints for the group to be considered more efficacious than placebo, thus maintaining an overall type I error rate of 0.05.

For each linzagolix group that is statistically significantly more efficacious than placebo for the co-primary endpoints, a fixed-sequence testing strategy shall be used within the group to test the ranked secondary endpoints as ordered in Section 2.5.1.2, to maintain the family-wise type I error rate. That is, the comparison for each linzagolix group versus placebo for each ranked endpoint will only be declared statistically significant different if the raw p-value multiplied by two is less than or equal to 0.05 for that endpoint and for all preceding endpoints for that dose versus placebo.

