4.8.3. Bone Mineral Density (BMD) by DXA

BMD of the femoral neck, total hip and lumbar spine will be assessed by DXA at Baseline, Month 6 and Month 6 follow-up. Unacceptable DXA assessments (accepted="No") will not be summarized (hip, and spine and femur considered separately).

In case of repeated values due to BMD loss \geq 5%, the initial scan will be used in summaries. Initial and repeated scan values will be reported in the listings.

Calibrated values should be provided once all cross-calibration data are made available to the vendor in charge of the scan assessment. These calibrated values will be used in the summary tables if available, otherwise initial values will be considered.

BMD values and corresponding Z-scores will be summarized for each treatment group. The within-group percent changes from baseline for BMD values will also be summarized, including 2-sided 95% confidence intervals.

Percent change from baseline to Month 6 and Month 6 follow-up will be described and will also be summarized in categories of percent change with the following classes:

- No change or increase,
- Decrease ≤ 3%,
- Decrease > 3% and $\leq 5\%$,
- Decrease > 5% and \leq 7%,
- Decrease > 7% and \leq 8%,
- Decrease > 8%.

The percent changes from baseline to Month 6 will be compared between each of the linzagolix groups and the placebo group via analysis of covariance with treatment group as the main effect (three values) and including the baseline as a covariate.

Sample SAS code (SAS code will be fully validated at the analysis stage) for analysis of covariance:

```
Proc GLM data=dataset order=internal;
        Class Treat;
        Model BMD_pchg = BaselineBMD Treat;
        LSMEANS Treat / at means pdiff= control('1') alpha=0.05 cl adjust=bon;
        ODS OUTPUT lsmeans=lsm diff=pvals lsmeancl=lsmeancl
lsmeandiffcl=lsmeandiffcl;
Run;
```

All data will be listed.

A listing of BMD for subjects who discontinued treatment will be provided.

CRS-BS-TP-000005 V 1.0

Page 93 of 127

Cytel Confidential: This is a controlled document and shall not be changed, saved, copied or reproduced by any unauthorized

Sponsor:	ObsEva		
Protocol:	18-OBE2109-003		
Document Version No.:	V5.0	Document Date:	13-JUN-2022

Subgroup analyses by race, age groups 1 and 2, weight and BMI groups 1 and 2 will be performed for BMD, including descriptive summaries, percent changes categories summaries and analysis of covariance.

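### The efficacy Bonferroni correction is carried into the between-arm BMD comparison, which modestly lowers its sensitivity to a small real bone loss

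*SAP*

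**What the plan says.** SAP 4.2.5 sets one rule for the two comparisons with placebo: "raw p-values will be multiplied by two prior to comparing to 0.05", "along with corresponding 97.5% confidence intervals". It opens with "All statistical hypothesis tests and confidence intervals will be two-sided" and exempts no safety endpoint. Protocol 13.1 states the same rule.

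For BMD, SAP 4.8.3 and protocol 13.5.5 describe an analysis of covariance of percent change at Month 6, each linzagolix group against placebo, with baseline as covariate. Neither text mentions an adjustment for that comparison. For within-group changes both specify an interval level: "including 2-sided 95% confidence intervals" in the protocol, with equivalent wording in the SAP. The adjustment enters SAP 4.8.3 only through the code: "LSMEANS Treat / at means pdiff= control('1') alpha=0.05 cl adjust=bon". That code is introduced as "Sample SAS code (SAS code will be fully validated at the analysis stage) for analysis of covariance".

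The sites are lumbar spine, femoral neck and total hip. SAP 4.8.3 repeats the analysis of covariance by race, age, weight and BMI groups. BMD is listed first among the safety endpoints (SAP 2.5.3, protocol 7.2) and is not among the ranked secondary endpoints (SAP 2.5.1.2).

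**The concern.** The stated purpose of the correction is to hold the overall type I error at 0.05 across two comparisons. For efficacy that guards against a false claim of benefit. For a harm the conservative direction is reversed: a stricter threshold and a wider interval make a true loss less likely to be declared. Nothing in the efficacy sequence depends on BMD, so nothing is gained in exchange.

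Small differences are where this could matter. The rationale for 75 mg without add-back therapy is that its effect on bone is limited (protocol 5.3 and 5.6), and a limited effect is the kind that a modest loss of power can hide. A reader of the BMD results would also meet 95% intervals within arms and 97.5% intervals between arms, and nothing in the text of SAP 4.8.3 gives notice of it.

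**Working it through.** **The plan's own level.** SAP 4.1 states "An overall two-sided type I error of 0.05 will be used", and there are two comparisons with placebo.
- Alpha per comparison: 0.05 / 2 = 0.025, so each interval is 1 − 0.025 = 97.5%. This reproduces SAP 4.2.5.
- Applied to the two differences from control, `adjust=bon` with `alpha=0.05` gives the same level: doubled p-values and 97.5% limits per comparison.

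**Effects that need no SD.**
- Normal critical values are 1.960 (unadjusted) and 2.241 (adjusted). The ratio is 2.241 / 1.960 = 1.144, so adjusted intervals are 14.4% wider. With t on 446 df the values are 1.965 and 2.249, with the same ratio.
- Let δ = true difference / SE. Power lost is Φ(δ − 1.960) − Φ(δ − 2.241). It is largest at δ = 2.10, where power falls from 55.6% to 44.4%, a loss of 11.2 points.
- Difference detectable with 80% power: (2.241 + 0.842) / (1.960 + 0.842) = 1.10, so 10% larger. Restoring that power would take 1.10² = 1.21 times the sample.

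**Illustration for a small difference.** The documents give neither the SD of percent BMD change nor the number expected to have an evaluable Month 6 scan. Assume 130 per arm (150 are randomised) and SDs of 2% to 3%. Take a true difference from placebo of 0.8 points. SE = SD × √(2/130) = SD × 0.1240.

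| Assumed SD | SE | 0.8 / SE | Power at 0.05 | Power at 0.025 |
|---|---|---|---|---|
| 2.0% | 0.248 | 3.22 | 89.7% | 83.7% |
| 2.5% | 0.310 | 2.58 | 73.2% | 63.3% |
| 3.0% | 0.372 | 2.15 | 57.5% | 46.4% |

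With all 150 per arm evaluable and SDs of 2%, 3% and 4%, power is 93%, 64% and 41% unadjusted against 89%, 53% and 31% adjusted.

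**A large difference.** At 2.6 points with 130 per arm and SD 3%, 2.6 / 0.372 = 6.99, and power is about 100% at either level.

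**When an observed 0.8 points would change status.** This needs 0.8 / SE between 1.960 and 2.241. With 130 per arm the SD must lie between 0.8 / (0.1240 × 2.241) = 2.88% and 0.8 / (0.1240 × 1.960) = 3.29%.
- SD 3.0%: p = 0.032, doubled 0.063.
- SD 2.5%: p = 0.010, doubled 0.020.
- SD 2.0%: p = 0.0013, doubled 0.0025.

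**The case against.** The strongest defence is that little hangs on this p-value. The plan sets no BMD hypothesis, margin or success rule. Point estimates are unchanged, the within-arm 95% intervals and the categories of percent loss (up to more than 8%) are unaffected, and individual women are covered by the discontinuation rule on BMD loss or Z-score, not by a test between arms. All of that stands, and it keeps the point modest.

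Mixed interval levels are also the plan's habit: SAP 4.6.2.1.2 gives 97.5% intervals for odds ratios and 95% for arm proportions. So the mixture is not peculiar to BMD, although it does need stating there.

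A wider interval is more cautious for ruling out a loss. With 130 per arm, SD 3% and an observed −0.8, the lower limit moves from −1.53 to −1.63. That is true, but the upper limit moves from −0.07 to +0.03, and the doubled p-value works only against flagging a loss.

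The code is labelled as a sample. That makes it easy to change, but SAP 4.2.5 and protocol 13.1 point the same way, so it cannot be put down to a stray option.

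A reader might infer that the correction would turn the Phase 2b bone loss at 75 mg into a non-significant result. The documents do not support this. Protocol 5.5.3 reports that spine result, at the site of "greatest bone loss) of -0.8% (95% CI -1.57, -0.03) after 6 months of treatment", as a change from baseline within the 75 mg arm, and gives no placebo BMD figure. It is not a difference from placebo, and the SAP would still report a change of that kind with a 95% interval. The change of status computed above also needs an SD in a narrow assumed band.

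**Conclusion.** The point holds as a modest reporting matter. The between-arm BMD comparison would be run at 0.025 with 97.5% intervals, for a harm endpoint where the correction protects no efficacy claim. The doubling, the 14% wider intervals and the ceiling of about 11 power points follow from the plan's own rule. The power figures for 0.8 points rest on assumed SDs and an assumed 130 evaluable women per arm. The differences of 0.8 and 2.6 points are illustrations: both echo Phase 2b changes within an arm, and the larger one came from 200 mg without add-back therapy, unlike the 200 mg arm here.

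A reader might also take BMD to be the trial's main safety endpoint. The documents list it first and plan a model between arms for it, while adverse events get no formal testing (SAP 4.8.2), but they do not rank safety endpoints. Nor do they support the view that a large bone loss would be missed: near 2.6 points the correction makes no practical difference.

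**What to change.** - **SAP 4.8.3:** report unadjusted two-sided 95% intervals and nominal p-values for each linzagolix arm against placebo at lumbar spine, femoral neck and total hip, removing `adjust=bon` from the code that produces them. Bonferroni-adjusted results may be kept alongside. State the interval level in the text.
- **Subgroup repeats:** give unadjusted estimates with 95% intervals. Nominal p-values are not needed there and would add many uncontrolled tests.
- **SAP 4.2.5:** state that the Bonferroni rule applies to efficacy comparisons only. Record this in SAP section 5 as a change from protocol 13.1. Editing 4.8.3 alone would leave it in conflict with both.
- **If Month 6 tables already exist:** add the unadjusted results beside the adjusted ones and say when they were added.

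The cost is one code option and a few sentences, with no new data and no effect on error control for the co-primary or ranked secondary endpoints. The downside is that BMD differences may look slightly less favourable, and nominal p-values carry a somewhat higher risk of a false signal.

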4.8.4. Laboratory Data

Clinical laboratory values will be expressed using conventional SI units.

Hematology, coagulation parameters, chemistry and lipids are assessed at screening and at each visit during the treatment period, as well as at M1 FU and M3 FU visits. E2, progesterone (P4) and LH will be assessed at each visit during the treatment period (not at the screening visit), as well as at M1 FU and M3 FU visits. Serum levels of anti-müllerian hormone (AMH) and fasting glucose will be assessed on Day 1 only. Serum levels of sex hormone-binding globulin (SHBG) will be assessed on Day 1 and Month 3 and Month 6 visits. Follicle-Stimulating Hormone (FSH) will be assessed at Month 3 FU at local laboratories for subjects who did not resume menses.

Blood samples will be analyzed by the central laboratory. Due to the COVID-19 situation, some samples may be collected by local laboratories.

Laboratory parameters values will be summarized for each visit for each treatment group and overall including within-group changes from baseline. In the event of repeated values, the last non-missing value per study day/time will be used.

Semi-quantitative laboratory results will be imputed as follows: "<X.X" will be imputed as "X.X/2" and ">X.X" will be imputed as "X.X".

Evaluation of shifts for changes from baseline to all visits, according to the normal ranges with categories "Low", "Normal", "High" where available (for ALT, AST, ALP, Bilirubin, Albumin, Calcium, Creatine Kinase) and according to normal/abnormal/abnormal clinically significant information collected otherwise, will be provided.

For Liver Function Test (LFT) parameters (ALT, AST, ALP, total bilirubin, albumin), evaluation of shifts for changes from baseline to the worst (highest) on-treatment value (including unscheduled assessments) according to the normal ranges with categories "Low", "Normal", "High" will be provided.

Assessments from local laboratories will not be included in summaries and shift tables, as normal ranges may not be comparable.

Sponsor:	ObsEva			
Protocol:	18-OBE2109-0	18-OBE2109-003		
Document Version No.:	V5.0	Document Date:	13-JUN-2022	

All laboratory data will be provided in data listings.

A subset listing will be presented for all abnormal clinically significant laboratory values.

For the lipid panel (Triglycerides, HDL, LDL, Total Cholesterol, LDL/HDL ratio), the percent change from baseline to each on-study visit will also be summarized.

For serum levels of E2, P4, SHBG and LH, only the actual values at each time point will be summarized. Note: in the event of repeated values, the last non-missing value per study day/time will be used.

In addition, for E2, the proportion of subjects with the following categories:

- E2 <20 pg/mL,
- E2 between \geq 20 and <60 pg/mL,
- E2 ≥60 pg/mL

at each visit and for each treatment group will be provided in tables and graphically (bar charts).

The relationship between E2 serum levels and bone mineral density loss will be explored graphically in different ways:

- First, the E2 serum level measured at Month 6 will be plotted on the x-axis against the percent BMD change measured at Month 6 on the left side y-axis and the percentage of subjects with clinically meaningful reduction of DYS (resp. NMPP) with stable or decreased use of analgesics for EAP on the right side y-axis.
- Second, bar charts will be produced at each visit up to Month 6 and presented with the percent BMD change from baseline to Month 6 on the y-axis and the proportion of subjects with the E2 categories described above on the x-axis. Similar graphs will be produced for each of the BMD sites (femoral neck, hip, and spine).
- Lastly, bar charts of the proportion of subjects with the E2 categories described above on the xaxis will be plotted against the percentage of responders according to the primary endpoint.

For P4, since P4 above 10 nMol/L may suggest luteal activity and hence ovulation, the proportion of subjects with P4 >10.0 nMol/L at least once from Study Day 1 to Month 3, from Month 3 to Month 6, and from Study Day 1 to Month 6 will also be provided in tables and graphically (bar charts).

The number and percentage of subjects at the following categories

- LDL ≥ 160 mg/dL
- LDL ≥ 190 mg/dL
- HDL < 40 mg/dL

Sponsor:	ObsEva		
Protocol:	18-OBE2109-003		
Document Version No.:	V5.0	Document Date:	13-JUN-2022

will be reported at each visit.

Shift tables from baseline to each visit will be provided for the following LDL and Triglycerides categories (after rounding to integer values if necessary).

LDL:

- 0: ≤ 130 mg/dL
- 1: 131 to 159 mg/dL
- 2: 160 to 189 mg/dL
- 3: ≥ 190 mg/dL

Triglycerides:

- 0: ≤ 150 mg/dL
- 1: 151 to 300 mg/dL
- 2: 301 to 500 mg/dL
- 3: 501 to 1000 mg/dL
- 4: >1000 mg/dL

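### The per-subject worst-value liver shift table takes the highest value as worst for albumin, which is the wrong direction; the shift tables also omit local-laboratory results on a reason that fits numeric summaries only

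*SAP*

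**What the plan says.** SAP 4.8.4 (Laboratory Data) plans several outputs that bear on liver parameters.

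- Numeric summaries: "Laboratory parameters values will be summarized for each visit for each treatment group and overall including within-group changes from baseline".
- A by-visit shift table: "Evaluation of shifts for changes from baseline to all visits, according to the normal ranges with categories 'Low', 'Normal', 'High' where available". Albumin is one of the seven analytes named for it.
- A per-subject worst-value shift table. It opens "For Liver Function Test (LFT) parameters (ALT, AST, ALP, total bilirubin, albumin" and specifies "evaluation of shifts for changes from baseline to the worst (highest) on-treatment value", with unscheduled assessments included and Low/Normal/High categories. The direction is given once for all five parameters, with no exception for albumin.
- Listings: "All laboratory data will be provided in data listings", and "A subset listing will be presented for all abnormal clinically significant laboratory values". Neither excludes local results.

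On local laboratories the section says "Due to the COVID-19 situation, some samples may be collected by local laboratories", and then "Assessments from local laboratories will not be included in summaries and shift tables, as normal ranges may not be comparable". The V5.0 entry in the SAP Section 5 change table explains the exclusion as a matter of not pooling local with central data in numeric summaries.

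Two rules elsewhere matter. SAP 4.2.9 moves an unscheduled safety assessment to a planned visit only if it lies within 14 days of that visit and the visit has no assessment of its own. Protocol 10.4.8 sends clinically significant laboratory abnormalities to adverse event reporting.

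**The concern.** A worst-value table exists to show, once per subject, the most adverse result she had on treatment. For ALT, AST, ALP and total bilirubin that is the highest value. For albumin, read as a marker of liver function, it is the lowest. Applying the highest-value rule to albumin turns the row into a best-value row under a worst-value label. A reader comparing arms would see almost no one move to Low whatever had happened.

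The second issue is the exclusion of local results from the same table. Protocol 5.5.3 reports that a few subjects on linzagolix had transaminases above three times the upper limit, most often returning to normal on treatment, and Protocol 5.7 calls the increases transient. A per-subject peak table is the output suited to catching such a rise. SAP 4.8.4 plans no table of multiples of the upper limit, so the worst-value table is the only per-subject peak summary of liver tests in that section. An elevation measured only locally would not be counted in it.

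**Working it through.** The plan gives no figure to reproduce. The check is a reading of the rule, followed by an illustration of its size.

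**1. What the rule does to albumin.** The highest of a set of values is below the lower limit only if all of them are. With one normal value among the included ones, the subject is classed Normal however many others were low.

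**2. How many values.** Protocol 10.2.2 and Appendix A schedule chemistry at Months 1 to 6. SAP 4.2.11 keeps Month 6 assessments in the main-study by-visit analyses. That gives six scheduled values, before any unscheduled ones.

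**3. Illustration.** Let p be the probability that a single visit's albumin is Low. The documents do not give p or the within-subject correlation, so both are assumptions. With independent visits:

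- highest-value rule: P(shown Low) = p^6
- lowest-value rule: P(shown Low) = 1 − (1 − p)^6

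For p = 0.05 these are 0.05^6 = 0.000000016 and 1 − 0.95^6 = 0.265. For correlated visits, equicorrelated normal values were simulated for 400,000 subjects per setting.

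| p | Correlation | Shown Low, highest-value rule | Shown Low, lowest-value rule |
|---|---|---|---|
| 0.01 | 0 | about 0% | 5.9% |
| 0.01 | 0.5 | 0.005% | 4.6% |
| 0.01 | 0.8 | 0.1% | 3.1% |
| 0.05 | 0 | about 0% | 26.5% |
| 0.05 | 0.5 | 0.1% | 18.5% |
| 0.05 | 0.8 | 0.9% | 12.5% |
| 0.10 | 0 | about 0% | 46.9% |
| 0.10 | 0.5 | 0.4% | 32.0% |
| 0.10 | 0.8 | 2.4% | 22.3% |

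In every setting the table as defined misses most of the subjects who had at least one low value.

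**4. What the other outputs recover.** A subject low at five central-laboratory visits and normal at one is counted Low in five of the six by-visit shift tables, and her values enter the by-visit summaries. Those outputs do not say how many different subjects were ever low. They also need not contain unscheduled values: under SAP 4.2.9, an unscheduled low albumin near a visit that has its own result is not assigned to that visit. The worst-value table, which does take in unscheduled assessments, would be the natural place to count it, but the highest-value rule discards it if any other included value is normal.

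**5. Local results.** A Low/Normal/High category is already relative to a reference range. Ranges that differ between laboratories are a good reason not to average the numbers. They are not a reason against classing each result by the range of the laboratory that produced it. The liver withdrawal rules in Protocol 10.7.2.1 and SAP 2.3 work in this range-relative way for ALT, AST and bilirubin, as multiples of the upper limit. The number of local samples is not stated, so the size of this loss cannot be computed.

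**The case against.** The strongest reply is that little disappears. The sentence just before the disputed one plans a by-visit shift table that names albumin, and the summaries cover every visit. All laboratory data are listed, clinically significant abnormalities have their own listing, and Protocol 10.4.8 and 12.1.2 route them to adverse events, which SAP 4.8.2 tabulates by group. This stands, and it limits the point.

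Three stronger readings are therefore not supported. A reader might infer that falls in albumin are hidden, or that only women low at every visit would be seen. That is true of one table, not of the plan. A reader might infer that locally measured elevations vanish. They lose their place in tabulated laboratory counts but remain in listings and, if clinically significant, in adverse events. A reader might infer that liver withdrawal decisions are affected. Albumin is not among those criteria, and they are applied during the trial, not from an end-of-study table.

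On local results the reply has further weight. The exclusion is stated openly with a reason. SAP 4.6.5.4 reports very few COVID-19 protocol deviations, although that is not a count of local samples. Protocol 10.4.8 mentions filing only central-laboratory reference ranges, and nothing in either document confirms that local ranges were captured. The remedy for this half may therefore not be available for every sample.

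None of this defends the albumin direction, which remains wrong as written.

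**Conclusion.** The albumin rule is an error in the stated definition. It rests on one premise from general knowledge, that low is the direction of concern for albumin as a liver marker, and otherwise on the wording alone. The percentages above illustrate its size and are not estimates for this trial.

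The local-laboratory point is secondary. The reason given does not extend to range-based categories, but the number of results involved is unknown and the remedy depends on what was recorded. The difference in wording between the change table and SAP 4.8.4 is not itself counted as a fault.

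The impact is small: one descriptive safety table, with no hypothesis test and no bearing on the co-primary endpoints, the ranked secondary endpoints, type I error or the bone density analysis. It is worth correcting because a table labelled worst value should show it.

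**What to change.** In SAP 4.8.4, replace the single direction with: the worst on-treatment value is the lowest for albumin and the highest for ALT, AST, ALP and total bilirubin, unscheduled assessments included. This costs one sentence and a minor change to one table program.

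For local results, first establish whether the local reference range was recorded with each value. Where it was, class the result by that range in the worst-value table, or in a sensitivity version of it, and keep local values out of numeric summaries as now planned. Where it was not, leave the value in the listings and give the number of excluded local liver results by arm in a footnote. The programming is modest if the ranges are in the database. If they would have to be collected from sites, the cost is higher, and the footnote alone would be a reasonable minimum.
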